Health professionals from both intervention and control centres will receive training sessions, targeting staff of the centres including nurses, medical doctors, and other technicians. The sessions will cover background information on each infection, including epidemiology, diagnostic tools, treatment available, particular aspects in high-risk groups such as immunosuppressed patients, data on cost-effectiveness, and screening recommendations for migrants.

Participants' selection

Therefore, when an individual comes to the PCC for any reason, the health professional will receive a message, in the EPR system, inserted as a pending task assignment with a recommendation on the diseases that should be considered for screening, based on this person's background characteristics. The tool is also able to identify if a person had already a diagnosis of any of the conditions included in the algorithm (based on ICD-10, International Classification Diagnosis codes) or if a diagnostic test had been performed for any condition included in the program. In such cases, the automated electronic prompt does not appear for that condition. A pilot test will be conducted with 3 health professionals to assure the correct functioning of the tool. In the control centres, we will hold just training sessions with the same screening recommendations as for the intervention centres but will not initiate the tool/prompts onto the EPR system. When the patient comes to the PCC, health professionals will decide what diseases/conditions should be screened for according to the information received either through the digital software (intervention centres) or based on their knowledge on the epidemiological background of the diseases (control centres), which was included in the training programme. In any case, health professionals will be responsible for requesting a blood test or a chest radiography and/or the derivation to a specialist.

Participant's selection for the feasibility and acceptability evaluation (focus group discussions, IDIs and survey)

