2.2 Specific Study Objectives

Primary objective 1: To compare the detection rate per month of all aggregated infections (HIV, HBV, HCV, TB, *T.cruzi*, *S.stercoralis* and *Schistosma spp.* infections) between the intervention and control centres over at least five years until the end of the intervention. In the Andalusian site, syphilis, latent TB and intestinal parasites will also be included.

Secondary objective 2: To compare the detection rate per month of each individual condition, the infections and FGM cases, between the intervention and control centres over at least five years until the end of the intervention.

Secondary objective 3: To compare the number of early HIV diagnoses between the intervention and control centres over at least five years until the end of the intervention.

Secondary objective 4: To compare the number of early HBV and HCV diagnoses between the intervention and control centres over at least five years until the end of the intervention.

Secondary objective 5: To compare the number of screening tests performed for all aggregated infections between the intervention and control centres over at least five years until the end of the intervention.

Secondary objective 6: To compare the number of screening tests performed for each individual condition between the intervention and control centres over at least five years until the end of the intervention.

Secondary objective 7: To estimate associations between the screening performance of all aggregated infections with different socio-demographic and epidemiological factors.

Secondary objective 8: To estimate associations between the screening performance of each individual condition with different socio-demographic and epidemiological factors.

Secondary objective 9: To measure the number of the diagnosed individuals with follow-up visits in the hospital of reference.

Secondary objective 10: To measure the number of the diagnosed individuals that have received treatment.

Secondary objective 11: To estimate the prevalence of each infection and FGM in the migrant population.

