Endpoint 6: The number of the screening tests performed for each individual condition will be compared between the intervention and control PCCs before and after the implementation.

Endpoint 7: Associations between the screening performance of the aggregated infections with different socio-demographic and epidemiological factors, such as, sex, age, geographic areas immunosuppression status, being attended in an intervention centre, fulfilling the screening criteria, among others, will be analysed.

Endpoint 8: Associations between the screening performance of each individual condition with different socio-demographic and epidemiological factors, such as, sex, age, geographic areas immunosuppression status, being attended in an intervention centre, fulfilling the screening criteria, among others, will be analysed.

Exploratory Endpoints

Endpoint 9: The number of migrant patients under follow-up in the hospital after a diagnosis of an infection or FGM will be estimated using the Minimum basic dataset (MBDS).

Endpoint 10: The number of migrant patients under treatment after a diagnosis will be estimated using the data from the EPR systems and MBDS.

Endpoint 11: The prevalence of each condition will be estimated using as the denominator the total number of tested migrant patients for that specific condition.

3. Study Methods

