intervention level. Linear regressions will be performed for the monthly detection rates of the aggregated infections, and of each individual condition, comparing the intervention and control centres before and during the intervention period.

- Other secondary outcomes will be the proportion of screening tests performed for the aggregated infections and for each individual condition, and factors associated with having a higher screening performance. For this, associations with continuous variables will be evaluated using t-tests, or one-way analysis of variance (one-way ANOVA) for normally distributed quantitative variables, while for not normally distributed quantitative variables, Wilcoxon Rank-Sum and Kruskal-Wallis tests will be carried out. Pearson's chi-square test or Fisher's exact test will be performed to evaluate the associations between categorical variables. In addition, odds ratio (OR) will be estimated (Table 3). Mixed effects logistic regression models will be carried out to identify associations between the screening performance and socio-demographic and epidemiological characteristics, and adjusted odds ratio (aOR) will be estimated, using the region of the PCC as a random intercept (Table 3).
- **b.** The **prevalence** of each individual condition will be estimated and reported with its respective 95%CI. The prevalence for each infection was defined as the number of diagnoses identified by the screening tests performed among the people that were tested. Serology tests will be contemplated for HIV, HBV, HCV, *T.cruzi*, *S.stercoralis* and *Schistosoma spp.* infections; for active TB, chest radiographies will be examined; for FGM, the completed questionnaires and/or referrals to specialists will be considered.

See table 4 for details of the methodology employed for the outcomes.

Data analysis in Andalusia

A similar analysis approach will be carried out in Andalusia but the limited number of PCCs may prevent to estimate the health impact of the tool, therefore, we plan to estimate preliminary effectiveness data. In addition, the analysis for syphilis, latent TB and intestinal parasites will be executed. Nevertheless, because the pilot study will be conducted in six PCCs of one area (Almería), we won't be able to carry mixed-effects logistic regression models and instead, multiple logistic regressions will be performed.

7. Tables and Figures

Table 1. Description of the ISMiHealth sample.

| Variables | Summary statistics | | |

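### Objective 11 asks for prevalence in the migrant population, but Endpoint 11 estimates positivity among those tested; the documents fix neither the size nor the direction of the difference

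*SAP*

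**What the plan says.** **Objective.** SAP section 2.2, Secondary objective 11, reads "To estimate the prevalence of each infection and FGM in the migrant population". The target population in SAP section 3.2 is migrants from Africa, Latin America, Asia and Eastern Europe who attend a participating centre.

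**Estimator.** In SAP section 2.3, Endpoint 11 says the prevalence of each condition "will be estimated using as the denominator the total number of tested migrant patients for that specific condition". SAP section 6 (Data analysis in Catalonia, item b) defines it for each infection as the "number of diagnoses identified by the screening tests performed among the people that were tested", and says the prevalence "of each individual condition will be estimated and reported with its respective 95%CI". Table 4 repeats this numerator and denominator. No weighting, standardisation, bounds or sensitivity analysis is given for this endpoint, and the calendar window of the tests that count is not stated.

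**Who gets tested.** Protocol section 5 says the tool is "able to identify if a person had already a diagnosis of any of the conditions included in the algorithm", or "if a diagnostic test had been performed for any condition included in the program". It continues: "In such cases, the automated electronic prompt does not appear for that condition". For control centres the study "will not initiate the tool/prompts onto the EPR system"; they receive training with the same recommendations. Protocol Annexes 1 and 2 set the recommendations mainly by country of origin, with further limits for some conditions. In Catalonia, for example, HIV testing is recommended for origins with prevalence above 1%. In Andalusia, Chagas testing is recommended for women aged 15–45 and for people who are, or may become, immunosuppressed, all from endemic countries. The clinician decides what to offer (Protocol section 8) and the patient may decline (sections 7g and 8).

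**The concern.** The objective names one population and the estimator uses another. The tested group is reached through origin criteria, then a prompt that exists in one arm only, then a clinician's choice and a patient's consent. SAP section 5.2 itself expects both detection and screening performance to be higher in migrants from endemic or high-prevalence areas, so testing is expected to be related to disease.

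If the plan is followed exactly, a figure labelled prevalence will be published with a 95% confidence interval. That interval covers sampling error only and says nothing about who was tested. Positivity could also differ between arms because prompting changes who is tested, and a reader could take that for a difference in disease.

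**Working it through.** **Plan's own figure.** There is none to reproduce. The documents give no expected prevalence, number tested or precision target for Endpoint 11. The only design figure (32 or more centres, a difference of 2, SAP section 4) concerns the detection rate.

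**Assumed inputs.** None of these is in the documents, so each is shown over a range:
- p: true prevalence, 2% for illustration.
- e: share of the target population eligible for the test.
- RR: prevalence in eligible people divided by prevalence in non-eligible people.
- s1: share of infected people not prompted (known diagnosis or earlier test).
- s0: share of uninfected people not prompted (earlier negative test).

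Each result is the ratio of expected positivity to true prevalence; 1.0 means no bias.

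**Step 1: origin targeting alone.** If only eligible people are tested, and at random among them, the ratio is 1/(e + (1 − e)/RR).
- e = 0.3, RR = 5: 1/(0.3 + 0.7/5) = 1/0.44 = 2.3.
- e = 0.3, infection confined to eligible people: 1/0.3 = 3.3.
- e = 1 (universal recommendation): 1.0.

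Protocol Annex 2 makes HIV, syphilis and HCV screening universal in the Andalusian target population, so this mechanism should contribute little there. It should contribute most where criteria are narrow.

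**Step 2: people not prompted, alone.** If unprompted people are not tested in the window and everyone else is tested at one rate, the ratio is (1 − s1)/[p(1 − s1) + (1 − p)(1 − s0)]. With p = 2%:

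| s1 | s0 = 0 | s0 = 0.2 | s0 = 0.5 |
|---|---|---|---|
| 0.2 | 0.80 | 1.00 | 1.58 |
| 0.5 | 0.51 | 0.63 | 1.00 |
| 0.7 | 0.30 | 0.38 | 0.60 |
| 0.8 | 0.20 | 0.25 | 0.40 |

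When s1 = s0 the ratio is exactly 1.0. For small p, a threefold understatement needs s1 ≈ 1 − (1 − s0)/3. That is 67% of infected people already known or tested if s0 = 0, 73% if s0 = 0.2, and 83% if s0 = 0.5.

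**Step 3: both together.** Take e = 0.3, RR = 5 and p = 2%. Prevalence among eligible people is 5 × 0.02/(0.3 × 5 + 0.7) = 4.55%.
- s1 = 0.5, s0 = 0.2: 0.0455 × 0.5/(0.0455 × 0.5 + 0.9545 × 0.8) = 2.89%, ratio 1.45.
- s1 = 0.8, s0 = 0.2: ratio 0.59.
- s1 = 0.66, s0 = 0.2: 0.01545/(0.01545 + 0.76364) = 1.98%, ratio 0.99. The two biases nearly cancel.

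**Step 4: in counts.** Take 10,000 migrants, all eligible, of whom 200 are infected (2.0%). Let 160 of the infected be already known (s1 = 0.8) and 1,960 of the 9,800 uninfected be tested earlier (s0 = 0.2).
- Still prompted: 40 infected + 7,840 uninfected = 7,880. Positivity is 40/7,880 = 0.51%.
- Restoring the known cases only: 200/(7,880 + 160) = 200/8,040 = 2.5%.
- Restoring known cases and earlier negatives: 200/10,000 = 2.0%.

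A control centre that tested the same population without regard to history would report about 2.0%, against 0.51% in the intervention centre, with identical disease.

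**The case against.** The strongest reply is that nothing is hidden. The SAP states the denominator in three places, and Endpoint 11 is listed as exploratory (although section 2.2 calls the objective secondary). Tables 1 and 2 report numbers meeting criteria, tested and diagnosed for each condition, and Endpoints 7 and 8 model who is tested, including by arm and by eligibility. This stands as a reason to treat the point as modest. It does not make the ratio answer Objective 11.

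Four stronger readings are tempting, and the documents do not support them:
- **That the published figure will be wrong several-fold.** Every magnitude above rests on assumed values, and the biases can cancel.
- **That control-centre testing is driven by clinical suspicion.** Protocol section 5 says control clinicians decide from their knowledge of the epidemiological background, after the same training. Selection on infection itself is possible in either arm, but it is not described.
- **That known cases drop out and so prevalence must be understated.** People with an earlier negative test are not prompted either, which offsets the loss. Only the prompt is withheld, and only in intervention centres; retesting is not barred. If the test window reaches into the look-back, earlier positives may re-enter.
- **That the protocol will set these estimates against outside prevalence studies.** In Protocol section 7e the more natural reading is that the number of cases is compared.

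**Conclusion.** The mismatch is in the text and does not depend on any assumption: Objective 11 asks for prevalence in migrants, and the plan computes positivity among those tested. Because prompts exist in one arm only and are withheld after a diagnosis or an earlier test, the ratio can also differ by arm without any difference in disease.

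The size and sign of the error are open. With 30% of migrants eligible and infection confined to them, the ratio overstates about 3.3-fold. With 80% of infected and 20% of uninfected people already known or tested, it understates about fourfold. Equal earlier testing in both groups removes the second bias altogether. The right statement is that the bias can reach about threefold in either direction under plausible-looking but assumed values. The primary comparison is unaffected.

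**What to change.** **Needed in any case**
- Rename the quantity in Endpoint 11, SAP section 6 item b and the Table 4 row as *positivity among those tested*.
- State the calendar window of the tests that count.
- Report it by arm and by eligibility, using the alert variables in SAP Annex 1, with testing coverage (tested/eligible) beside it. Say whether those variables mark everyone who meets the screening criteria or only people still prompted after earlier diagnoses and tests are removed.

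**Then choose one**
- Reword Objective 11 to match; or
- Keep a prevalence objective but restrict it to the eligible population. Count people with a known diagnosis *and* people with an earlier negative test from the look-back. Restoring only the known cases overshoots (2.5% against 2.0% in the counts above).

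Any weighted estimate should be a sensitivity analysis with bounds. A weighting model should include eligibility; the four-level area of birth is too coarse to stand in for country-based criteria. Weighting cannot remove selection on unmeasured infection risk.

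**Cost.** The first part is SAP wording and a few table columns from variables already planned. The prevalence option needs dated test results. SAP Annex 1 lists tests as yes/no and shows no separate test date. The monthly detection rates imply that dates will be extracted, but this should be confirmed. The estimate becomes more modest in scope and its interval wider.

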3.1 Study design

A pragmatic cluster controlled randomised trial will be conducted in 35 PCCs of Catalonia to explore and assess the effectiveness of the digital tool ISMiHealth. Additionally, a pilot clustered controlled randomised trial will be conducted in Andalusia, implementing the ISMiHealth tool in six PCCs to explore preliminary effectiveness data. This user-friendly innovative digital tool (ISMiHealth) that aims to facilitate targeted screening to recently arrived migrants presenting for a routine appointment, will be integrated into the local EPR system of the intervention-PCCs of the two different settings of Spain (Catalonia and Andalusia). The tool will send real-time recommendations to health professionals concerning the screening of infectious diseases and female genital mutilation based in the individual risk of each migrant patients, using the

variables sex, age, and country of origin. Meanwhile, the control-PCCs will follow the routine care practice. All centres will receive training sessions on Migrant Health and Female Genital Mutilation.

The screening programme will be implemented in a real-life context in the selected PCCs, and the receivers/users of the tool will be all health professionals (general practitioners and nurses) working at those centres. On the other hand, the tool and the outcomes of the study will be evaluated in the migrant patients, the indirect beneficiaries of the tool.

3.2 Inclusion and exclusion criteria

Inclusion criteria of PCCs:

• Centres with a migration density higher than 7%

Inclusion criteria of PC professionals:

Aged >18 years old working at the selected PCCs

Inclusion criteria of migrant populations:

- Individuals assigned to a PCC
- Patients attending a PCC for any reason
- Aged ≥15 years old in the Catalonian site
- Aged >14 years old in the Andalusian site
- Coming from Africa, Latin-America, Asia and Eastern Europe following the categorization of the UN Statistical Commission¹³

Exclusion criteria:

- For the active TB recommendation, migrants residing in the host country for more than five years.
- For FGM recommendation, being a male.

3.3 Health centres selection, randomisation and masking

Regarding the selection of the participating PCCs in Catalonia, the Fundació d'Investigació en Atenció Primària Jordi Gol i Gurina (DIAP Jordi Gol) research team will find areas where there are referents with an interest in participating in the study. The list of PCCs belonging to these areas, where the referral to the reference laboratory is more feasible, will be provided. With this final list, we will proceed with the randomization stratified by area and by density of migrant population in the area (low, medium and high). For the selection of the PCCs in Andalusia, an IT committee of the Andalusian Health Service (SAS) will provide a list of the possible centres that could participate in the study and the randomization will be carried out using the same stratification method mentioned previously.

The randomization will be performed through a statistical software for each pair of selected health centres stratified by study area. Therefore, for each pair of PCCs, one PCC will be randomly selected to implement the screening programme through the ISMiHealth software, and it will be compared with the other PCC of the same area where the PCCs do follow the current practices in the routine care. In both cases, health professionals will receive a training session on migrant health; the training contents will include for each condition, epidemiological aspects, diagnosis, treatment and the screening recommendation.

3.4 Study Variables

Data will be collected retrospectively, therefore, the data for all the variables mentioned in Annex 1 will be collected after the year of intervention is completed.

4. Sample size calculation

Considering that all PCCs included in the study have a migration density higher than 7%, we have estimated that by including 32 or more centres in Catalonia we will achieve a difference in difference detection rate of all aggregated infections between intervention and control centres of 2, with a 95% precision. A comparative analysis of the PCCs, in relation to the migration density, will be first performed to select the pairs of centres; then, each pair of selected health centres will be randomized, stratifying by study area, using the Statistical software Stata. To assure the validity of results the intervention centres (where the ISMiHealth tool will support the clinicians' decisions) will be compared to the control centres (where the routine care will be followed) with more similar characteristics.

41 PCCs will participate, 35 in the Catalonian site and six in the Andalusian site. In Catalonia 18 PCCs will be intervention and 17 control, not pairing one of the centres; while in Andalusia there will be 3 intervention and 3 control PCCs. The users of the ISMiHealth tool will be the health professionals of the intervention centres and as participants of the study, they will decide whether to follow the recommendations to screen migrant patients, the indirect beneficiaries of the tool. Approximately 980 health professionals will participate in the study.

5. General Considerations

5.1 Timing of Analyses

In the Catalan Institute of Health, data will be extracted retrospectively after the year of implementation from the EPR system (eCAP) by the Information Technology (IT) staff of the Sistema d'Informació per al Desenvolupament de la Investigació en Atenció Primària (SIDIAP). The study variables will be pseudo-anonymized, with technical and functional separation, by a SIDIAP data manager. SIDIAP will be responsible for the data processing in Catalonia. Regarding SIDIAP source data, the strict SIDIAP security standards will be followed.

In Andalusia, the data will be extracted retrospectively after the year of implementation by a specialized IT committee of the Andalusian Health Service Institution of the area involved in this project (Almería). The information will be extracted retrospectively and will include: 1) the check-list from the tool and 2) the demographic and clinical variables. Then, the IT committee will link this information with the laboratory data of the reference hospital (Hospital de Poniente in Almeria) and will pseudo-anonymize the data.

Thereafter, the biostatistician responsible for the data analysis will have access to the pseudo-anonymized data. The pseudo-anonymized data, which will be analysed after the year of intervention is completed, will include the variables detailed in Annex 1 for the targeted migrant population of the PCCs of Catalonia and Andalusia included in the study.

In any case, the data from the Catalonian centres will be analysed separately from data of the PCCs from Almeria where a process evaluation will be performed and only preliminary effectiveness data will be estimated.

